### 7.2.4 Safety Follow-up Visit(s)/End of Study Visit

All subjects, including subjects who withdraw early, should complete a safety follow-up visit 30 (± 3) days after the last dose of blinatumomab, or prior to HSCT or any non-protocol specified anti-tumor therapy, if applicable. The following procedures will be completed at the visit:

- ECOG Performance Status Assessment (adult subjects only; Appendix E)
- Karnofsky/Lansky Performance Status Assessment (pediatric subjects only; Appendix J and Appendix K, respectively)
- Complete neurological examination
- Bone marrow aspirate/biopsy (morphological)
- Physical examination as per standard of care
- Vital signs (eg, blood pressure, heart rate, respiration rate, temperature)
- Weight

Date: 20 March 2019 Page 72 of 122

- Local laboratory assessments including:
  - Chemistry

Product: Blinatumomab

- Hematology with differential
- Urinalysis via dipstick
- Urine or serum pregnancy test (females of childbearing potential)
- **Immunoglobulins**
- Central laboratory assessments including:
  - Immunogenicity sample: anti-blinatumomab antibody, HAMA
  - Lymphocyte subsets (Phase 1b/2 only; not required for subjects enrolled in the expansion cohort)
- Serious adverse event reporting
- Adverse event reporting
- Documentation of concomitant medications

### 7.2.5 Long-term Follow-up

Long-term follow-up is required for subjects participating in the Phase 1b/2 parts of the study. Long-term follow-up is not required for subjects participating in the expansion cohort. All subjects enrolled in Phase 1b/2 will be followed in the long-term follow-up portion of the study for survival. Subjects in remission will also be followed for duration of response. Following the safety follow-up visit, subjects will be followed via clinic or telephone contact at 3, 6, 9, 12, 18, and 24 months (± 2 weeks) after completion of the safety follow-up to assess disease status and survival. Subjects will allow Amgen/AABP continued access to medical records, so that information related to subjects' health condition including duration of response and survival may be obtained.

The following procedures will be completed for subjects who remain in remission at each clinic visit:

- Disease/survival status
- Bone marrow aspirate/biopsy (morphological)
- Local laboratory assessments including:
  - Hematology with differential
- Central laboratory assessments including:
  - Lymphocyte subsets (at 6 months after the safety follow-up visit if B cells have not recovered at the safety follow-up visit [ie, number of CD19-positive cells is 90 to 570 per µL])
- Documentation of concomitant medications (anti-leukemic treatments only)

Page 73 of 122

Product: Blinatumomab Protocol Number: 20130265 Date: 20 March 2019

The following procedures will be completed for subjects who did not respond to or relapsed after blinatumomab, who have received other anti-leukemic treatments or HSCT, and are being followed in long-term follow-up:

Telephone contact by either the research investigational site or treating physician to the subject to determine survival status

Documentation of concomitant medications (anti-leukemic treatments only)

Should a subject fail to return to the clinic for a scheduled protocol visit, or not be available for telephone contact, sites will need to make 3 attempts by a combination of telephone and mail to contact subjects. Sites must document all 3 attempts to contact the subject. If a subject does not respond within 1 month after the third contact the subject will be considered lost to follow-up and no additional contact will be required.

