f Immunoglobulin (IgG) samples will be collected pre-dose on D1, at D29 ± 8 days of each treatment cycle, and the SFU visit.

<sup>9 Anti-blinatumomab antibody and HAMA samples will be collected before first dose on D1; cycles 1 and 2 on D29: +6h after end of infusion; and at the SFU visit. See Section 7.3 for details regarding additional samples needed if anti-blinatumomab antibody sample is positive at SFU.

h Pharmacokinetics (adults): Cycle 1 only on D1: prior to infusion, and +2h, +6h, +10h after infusion start; D2: +24h after infusion start; D8: 0h (prior to dose step); D15: any time during infusion; D29: 0h (prior to stopping infusion), and then +1h, +2h, +4h, +6h after end of infusion. All other cycles on D8, D15, D29: any time during the infusion. Pharmacokinetics (pediatric): Cycle 1 only on D1: prior to infusion, and +2h, +10h after infusion start; D2: +24h after infusion start; D15: any time during infusion; D29: 0h (prior to stopping infusion), and then +2h, +6h after end of infusion. All other cycles on D8 any time during the infusion.

<sup>1Cytokines (adults): Cycle 1 only on D1: +2h, +6h, +10h after infusion start; D2: +24h after infusion start; D8: +2h, +6h, +10h after dose step. All other cycles on D1: +6h after infusion start. Cytokines (pediatric): Cycle 1 only on D1: +6h, +10h after infusion start; D2: +24h after infusion start; All other cycles on D1: +6h after infusion start.

j Lymphocyte subsets (adults): Cycle 1 only on D1: prior to infusion; D2: +24h after infusion start; D8, D15 and D29: any time during infusion. Lymphocyte subsets (pediatric): Cycle 1 only on D1: prior to infusion; D2: +24h after infusion start; D8, and D29: any time during infusion. For all subjects, if B cells have not recovered (number of CD19-positive cells is 90 to 570 per μL) at the SFU visit, lymphocyte subsets will also be collected 6 months after the SFU visit.

k Subject writing sample will be completed by adult subjects only, in the morning and evening on D1 and D2, then once daily for each cycle.

Serious adverse events collected from time of informed consent; adverse events collected from time of enrollment. Refer to Section 9 for adverse event/serious adverse event reporting guidelines.

Date: 20 March 2019 Page 65 of 122

<sup>m Concomitant medication documentation during long-term follow-up period is limited to only anti-leukemic treatments.

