#### 7.2.12 **Lymphocyte Subsets**

Lymphocyte subset testing is required for subjects participating in the Phase 1b/2 parts of the study. Lymphocyte subset testing is not required for subjects participating in the expansion cohort. Lymphocyte subsets will be measured by flow cytometric determination of different markers (eg, T cells: CD3, CD4, CD8; B cells: CD19; T cell subsets: CD45RA, CD197, and others). Lymphocyte subsets will be collected at time points outlined in the Schedule of Assessments (Table 6).

If B-cell counts have not recovered at the safety follow-up visit (recovered is defined as number of CD19-positive cells per µL is 90 to 570) (McNerlan et al, 1999), and the subject has not relapsed, another sample will also be taken 6 months after SFU visit for determination of lymphocyte subsets.

<sup>b At screening only.

<sup>c Not required for subjects enrolled in the expansion cohort.

Product: Blinatumomab Protocol Number: 20130265

Date: 20 March 2019 Page 79 of 122

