### **10.8.2 Pharmacodynamic Analysis**

The PD analysis will be based on the PD analysis set. Descriptive statistics or graphic presentation will be used for data analysis.

Lymphocyte subsets: Cell counts of each cell type tested at baseline and over time will be presented graphically. Summary statistics of cell counts may be presented if data are sufficient. Individual data will be provided as a listing.

Cytokines: Summary statistical analysis of cytokine levels (eg, IL-2, IL-4, IL-6, IL-10, TNF- $\alpha$ , IFN- $\gamma$ ) prior to treatment and during blinatumomab infusion will be provided for each sampling collection time. Maximal cytokine concentration (Cmax) of each cytokine will be summarized by descriptive statistics. Individual data will be provided as a listing.

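### The 6-month lymphocyte sample has contradictory triggers: Section 7.2.5 and Table 6 footnote j attach 90 to 570 CD19-positive cells per µL to non-recovery, Section 7.2.12 attaches it to recovery

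*Protocol*

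**What the plan says.** Three places in the current protocol state when the extra sample is due.

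- **Section 7.2.12 (Lymphocyte Subsets)** sets the rule and defines the term: "If B-cell counts have not recovered at the safety follow-up visit (recovered is defined as number of CD19-positive cells per" µL is 90 to 570), with a citation. It continues: "and the subject has not relapsed, another sample will also be taken 6 months after SFU visit for determination of lymphocyte subsets".
- **Section 7.2.5 (Long-term Follow-up)** lists the same sample among the procedures for subjects who stay in remission, to be taken "if B cells have not recovered at the safety follow-up visit [ie, number of CD19-positive cells is 90 to 570 per" µL.
- **Table 6, footnote j** asks for it in all subjects "if B cells have not recovered (number of CD19-positive cells is 90 to 570 per" µL) at the safety follow-up visit.

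On scope, Section 7.2.12 says: "Lymphocyte subset testing is required for subjects participating in the Phase 1b/2 parts of the study". The expansion cohort is exempt. Peripheral blood lymphocyte subsets are listed as a Phase 2 exploratory endpoint in both documents. SAP Section 10.8.2 plans a descriptive display: "Lymphocyte subsets: Cell counts of each cell type tested at baseline and over time will be presented graphically". Summary statistics are optional there, and individual data are listed. The definitions in SAP Section 6 do not include B-cell recovery, so the SAP does not settle which protocol wording governs.

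**The concern.** The same numerical range carries opposite labels. In 7.2.5 the abbreviation ie equates 90 to 570 with failure to recover; in 7.2.12 that range is what recovery means. If a site acts on the bracket in 7.2.5 or the footnote, a subject with a normal B-cell count is called back for a sample, while a subject with few or no B cells is not.

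This matters because the documents describe no other lymphocyte subset sample after the safety follow-up visit. It is the only scheduled look at late B-cell recovery. The protocol treats depletion as relevant: Section 2.3 links it to a possible rise in infections, and Section 2.4 reports that B-cell suppression lasted through the treatment-free interval. If sites resolve the conflict differently, the 6-month points on the SAP's graphs would come from two opposite selection rules, with nothing in the display to show it.

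**Working it through.** The plan gives no figure to reproduce, and no sample-size or error-rate formula applies. The check is a comparison of the three statements.

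**Step 1. Which label the range carries.**

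| Place | Condition for sampling | What 90 to 570 per µL is attached to |
|---|---|---|
| 7.2.12 | B cells not recovered, no relapse | Recovered (explicit definition) |
| 7.2.5 | B cells not recovered, subject in remission | Not recovered (joined by ie) |
| Table 6, footnote j | B cells not recovered, all subjects | Not recovered (parenthesis, no ie) |

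The verbal condition and the limits are the same in all three places. Only the meaning given to the range differs.

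**Step 2. Who is sampled under each reading.** The counts are illustrative, taken at the safety follow-up visit, in a subject who is in remission.

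| CD19-positive cells per µL | 7.2.12 | 7.2.5 or footnote j, bracket read literally |
|---|---|---|
| 0 | sample | no sample |
| 50 | sample | no sample |
| 200 | no sample | sample |
| above 570 | sample | no sample |

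The set sampled under 7.2.12 is every count below 90 or above 570. The set sampled under the literal bracket is every count from 90 to 570. Each is the complement of the other, so the two readings disagree at every possible count.

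**Step 3. Which label is the intended one.** Section 7.2.12 uses a defining phrase, "recovered is defined as number of CD19-positive cells per" µL being 90 to 570, and cites a source. The protocol's reference list shows that source to be a paper on reference intervals for lymphocyte subsets in healthy people. A healthy reference interval fits recovered and does not fit its opposite.

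**Step 4. Who can be affected.**

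- Phase 1b/2 only. Section 10.2 gives a planned maximum of 36 + 21 = 57 subjects.
- Section 7.2.12 removes subjects who have relapsed.
- Section 7.2.5 gives telephone contact only to subjects who did not respond, relapsed, or received HSCT or other anti-leukemic treatment. Table 6 footnote n does the same for non-responders and relapsed subjects.

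The remainder is a fraction of 57. The documents do not allow it to be put more exactly, because they give no distribution of CD19 counts at the safety follow-up visit.

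**Step 5. Eligibility.** The three places also differ on who is eligible. A non-responder, or a subject transplanted in remission, may not have relapsed and so meets the 7.2.12 condition, yet 7.2.5 gives that subject telephone contact only. Footnote j names all subjects; because that phrase follows separate adult and pediatric schedules, it may mean only both age groups, but it does not say so.

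**The case against.** The strongest reply is that all three places share one operative condition, that B cells have not recovered, and only the gloss differs. Section 7.2.12 is the section dedicated to this test, and it defines the term correctly. A site that follows it samples the right subjects. The parenthesis in footnote j has no ie and can be read as a reminder of the recovery range. This stands in part: the footnote is the softer of the two, and mis-sampling is a possibility that depends on how sites read the text. A reader might infer that the sample would in fact come from the wrong subjects throughout the trial. The documents do not show that.

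The reply does not remove the problem. Section 7 sends sites to Table 6 for the procedures at each visit, 7.2.12 itself refers to Table 6 for time points, and 7.2.5 is the list for long-term follow-up. The doubtful wording is therefore in the places used to run visits, and in 7.2.5 it allows no other literal reading.

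A reader might also infer that the trigger should simply be a count below 90. The documents do not support that either. Section 7.2.12 defines recovered by a two-sided range, so counts above 570 also fall outside it, and a one-sided threshold would be a new rule.

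Finally, it is fair to say that the stakes are low: one exploratory time point, presented descriptively.

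**Conclusion.** The contradiction is real and sits in current protocol text. Sections 7.2.5 and 7.2.12 cannot both be applied as written, and Table 6 footnote j sides with 7.2.5 on its face. Read literally, those two places could take the 6-month sample from subjects whose B cells have recovered and omit it in those still depleted.

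The size is minor. The point affects one follow-up time of a descriptive exploratory measure, in Phase 1b/2 subjects who have not relapsed. It does not reach CR/CRh*, DLT assessment, dose selection, the two-stage decision or the sample size. It is an internal inconsistency in wording, because the intended rule is stated in 7.2.12.

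The conclusion rests on two assumptions: that 7.2.12 carries the intended meaning, which its defining phrase and its source support, and that at least some sites might act on the bracket. Neither the number of subjects mis-sampled nor whether any were can be learned from the documents.

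**What to change.** 1. In Section 7.2.5 and Table 6 footnote j, replace the bracket with the 7.2.12 definition ("recovered is defined as number of CD19-positive cells per" µL is 90 to 570). The sample is then due when the count is outside that range.
2. State one eligibility condition in all three places. Choose between all subjects, those who remain in remission, and those who have not relapsed, and say explicitly what applies to non-responders and to subjects transplanted in remission.
3. The SAP's version history refers to a clinical study report for the primary analysis, so some 6-month samples may already exist. For these, compare each subject's CD19 count at the safety follow-up visit with whether a 6-month sample was taken, and report the rule actually applied beside the 6-month data.

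The cost is two wording corrections, one agreed eligibility phrase and a short data check on counts already collected. No change to the design or the planned analysis is needed. The number of samples may rise or fall slightly: a reader might expect the correction to be neutral, but that depends on counts the documents do not give.

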#### 7.2.6 **Neurological Examination**

A neurological examination will be performed as outlined in the Schedule of Assessments (Table 6). Subjects will be specifically queried for neurological symptoms observed in the interval since the last extended neurological examination. Abnormalities of the following should be recorded: level of consciousness, orientation, vision, cranial nerves and brain stem functions, pyramidal and extra pyramidal motor system, reflexes, muscle tone and trophic findings, coordination, sensory system, neuropsychological findings (eg, speech, cognition and emotion).

#### 7.2.7 **Subject Writing Sample**

Adult subjects will be asked to provide daily writing samples to detect early cerebellar signs as outlined in the Schedule of Assessments (Table 6). Subjects will write down the current date, current location and time in the sentence. The sentence format should be repeated each time throughout the study. Interpretation of writing sample results will be based solely on the investigator's assessment.

#### 7.2.8 **Lumbar Puncture and Intrathecal CNS Prophylaxis**

Please refer to Section 6.4 for mandatory intrathecal CNS prophylaxis guidelines.

Product: Blinatumomab

Date: 20 March 2019 Page 74 of 122

#### 7.2.9 Bone Marrow Biopsy/Aspiration

Bone marrow will be used for hematological assessment and for evaluation of MRD by PCR. The following samples will be obtained for cytomorphological assessment and MRD measurement:

- Cytomorphology: BM smears (slides) at screening and at the end of each treatment cycle. In case of insufficient quality of the aspiration material at the end of each treatment cycle, a core biopsy should be performed before treatment start in the next cycle or at the safety follow-up visit, if the subject has not progressed and no further treatment cycles are to be administered.
- MRD: aliquots for PCR (individual rearrangements), at screening (if not performed as part of routine testing) and at the end of the first and second treatment cycles will be collected and analyzed at a central lab.

If a marrow aspiration is not possible, or the aspirate does not contain any BM, a core biopsy will be done. In case of core biopsies, no central MRD assessment will be possible due to the need to preserve the biopsy with formalin before shipment.

If a subject has not relapsed by their last induction and consolidation treatment cycle, a BM biopsy or aspirate should be performed every long-term follow-up visit until relapse.

The degree of bone marrow infiltration defined by the percentage of leukemic blasts in bone marrow will be evaluated by local laboratories as per cytological assessment. In addition, the bone marrow slides will be provided to the designated central laboratories for hematological assessment. The B-precursor phenotype has to be confirmed by the central laboratory by immunocytochemistry. The following markers will be analyzed as needed: CD3, CD5, CD10, CD13, CD19, CD23, CD33, CD34, CD79A, POX, TDT.

The results of the local laboratory are applicable for inclusion into the study and for the decision if pre-treatment should be administered if the results of the central laboratory are not yet available at the time these decisions are made.

Known cytogenetic and molecular aberrations will be documented in the case report form (CRF).

Results of additional tests routinely conducted by the investigators, but not required by the protocol such as immunophenotypic, cytogenetic or molecular analyses conducted during the study, will be collected and documented in the CRF.

All BM assessments will be performed at time points outlined in the Schedule of Assessments (Table 6).

**Product: Blinatumomab** 

Date: 20 March 2019 Page 75 of 122

#### 7.2.10 **Definitions of Treatment Response**

#### 7.2.10.1 **Adult Subjects**

At screening and at the end of each treatment cycle a centrally analyzed bone marrow aspiration and local peripheral blood counts will be performed to evaluate the efficacy of protocol-specified therapy. Criteria for treatment response are defined in Appendix F.

Evaluation of CR and CRh\* will occur at the end of each treatment cycle as per the following definitions:

- CR is defined as ≤ 5% blasts in the bone marrow, no evidence of disease, and full recovery of peripheral blood counts: platelets > 100,000/µl and absolute neutrophil count (ANC) > 1,000/µl
- CRh\* is defined as ≤ 5% blasts in the bone marrow, no evidence of disease, and partial recovery of peripheral blood counts: platelets > 50,000/µl and ANC  $> 500/\mu I$

Subjects who develop isolated CNS leukemia relapse during treatment and who have not met the criteria for an event as defined above, may continue on study and receive additional CNS directed therapy in addition to their systemic protocol-specified therapy. Nevertheless, an isolated CNS event would be considered an event.

## **Extramedullary Disease**

An extramedullary relapse will be assessed as hematological relapse. If clinical signs of extramedullary lesions are present, assessments will be performed according to modified Cheson criteria (Appendix G). If computed tomography (CT) scans are conducted, this should be done according to standard clinical practice. If a CT scan has been performed within 14 days before start of blinatumomab treatment and if no clinical signs of a change of disease state have been observed, this assessment can be regarded as screening assessment.

#### 7.2.10.2 **Pediatric Subjects**

The treatment is defined to be efficacious, when the subject is stated to be in CR with recovery of peripheral blood counts, or in CR with incomplete recovery of peripheral blood counts. The onset of remission will be defined by the later of the date of the first marrow aspiration in which the remission was documented and the day in which peripheral blood count recovery met the defined criteria.

Protocol Number: 20130265

Date: 20 March 2019 Page 76 of 122

Hematological responses are defined by the following criteria (Lauten, 2012):

- Complete remission (CR) (including subjects with incomplete recovery of peripheral blood counts):
  - No evidence of circulating blasts or extra-medullary disease;
  - M1 bone marrow (≤5% blasts in an evaluable bone marrow).

CR subjects will be subclassified based on their peripheral blood counts

- M1 bone marrow with full recovery of peripheral blood counts:
  - o Platelets > 100 x 109/L and
  - $\circ$  ANC > 1.0 x 10 $^{9}/L$

Product: Blinatumomab

M1 bone marrow with incomplete recovery of peripheral blood counts:

Meets the criteria for CR except for full recovery of peripheral blood counts:

- Platelets > 50 x  $10^9$ /L but ≤  $100 \times 10^9$ /L and ANC >  $0.5 \times 10^9$ /L but ≤  $1.0 \times 10^9$ /L
- M1 bone marrow that did not qualify for full or incomplete recovery of peripheral blood counts

Hypocellular or acellular bone marrow:

- No M1 bone marrow MRD response
- MRD < 10-4 measured either by PCR or flow cytometry

- No evidence of disease
- Insufficient recovery of peripheral blood counts
  - Platelets  $\leq$  100 x 10^9/L or ANC  $\leq$  0.5 x 10^9/L

# Complete MRD response

No detectable signal for leukemic cells either by PCR or flow cytometry

## Partial remission

• Complete disappearance of circulating blasts and achievement of M2 marrow status (> 5% to < 25% blast cells) and appearance of normal progenitor cells.

